SUSAR	Suspected Unexpected Serious Adverse Reaction
THA	Total Hip Arthroplasty
TT	Trabecular Titanium
WMO	Medical Research Involving Human Subjects Act; in Dutch: Wet Medisch-wetenschappelijk Onderzoek met Mensen

SUMMARY

Rationale: Aseptic loosening of the acetabular component of hip implants in total hip arthroplasty (THA) remains one of the main causes of long-term implant failure and revision surgery. Aseptic loosening is often induced by wear of polyethylene liners, causing osteolysis around the implant. Highly cross-linked polyethylene liners have been developed to reduce wear. Ceramic-on-ceramic (CoC) shows even lower wear rates compared to ceramic on polyethylene CoP. However, the inelasticity of a CoC bearing might cause increased micromotion and thereby affect implant stability in press-fit THA.

The Delta TT cup and H MAX S stem have been developed aiming to optimize initial stability and osseointegration of the implant. In our initial Delta TT RSA study, the migration of Delta-TT cups with a H MAX S stem was compared, using Radiostereometric Analysis (RSA) between ceramic and polyethylene liners. The results at 2- and 5-years after the operation showed good stabilization of the implant, regardless of liner type. A trend towards increased migration was observed in Delta TT cups combined with ceramic liners, but the between-group effects were small and not statistically significant.

Objective: The primary objective of this 10-year follow-up study is to investigate long-term migration patterns of the Delta-TT cup, comparing outcomes between ceramic and polyethylene liners. Similar to the 2- and 5-years results, good stability is hypothesized at 10-years postoperatively, regardless of liner type.

The secondary objectives are to measure migration of the H MAX S stem at 10-years postoperatively, to evaluate implant survival, signs of osteolysis, clinical outcomes and patient-reported outcome measures (PROMs) for the Delta-TT cup and H MAX S stem, comparing outcomes between the ceramic and polyethylene group.

Study design: This is a long-term follow-up of a randomized control trial comparing migration patterns of the Delta-TT cup between ceramic and polyethylene liners.

Study population: Patients included in the initial Delta TT randomized study, will be invited to participate in this 10-year follow-up study. At the time of inclusion, patients were male or non-pregnant female, between 18 and 75 years of age, who provided informed consent for the initial Delta TT study and underwent uncemented total hip arthroplasty.

Study parameters/endpoints: the primary endpoint of this study is the long-term (10-year) stability of the Delta-TT cup, compared between a ceramic and polyethylene liner. This is

measured in 3D translations and rotations via RSA X-rays en mean migration results will be compared between the 2 groups.

Secondary endpoints include long-term (10-year) stability of the H MAX S stem, measured in 3D translations and rotations via RSA X-rays. Besides, implant survival and radiographic signs of osteolysis will be investigated for the Delta TT cup and H MAX S stem. Additionally, clinical outcomes such as squeaking and PROMs will be collected using questionnaires, including EuroQol 5D-5L (EQ5D-5L), Hip disability and Osteoarthritis Outcome Score-Physical function Short form (HOOS-PS), Numeric (Pain) Rating Scale (NRS) and Oxford Hip Score. Finally, we will compare the survival data at 10-years postoperatively with the predicted survival at 2-years postoperatively using the thresholds presented in the literature. The aim is to quantify how well RSA analysis at 2-years predicted survival for the uncemented press-fit components used in this study, based on migration and survival results of individual patients.

Nature and extent of the burden and risks associated with participation, benefit and group relatedness: Patients have already been randomized in the initial study between a polyethylene and ceramic liner and are being evaluated by means of RSA imaging and PROMs. There are, in our view, no risks associated with participation in this study. The added effective radiation dose for this study is 0.27 mSv. This is negligible when compared to the natural annual exposure of 2.9 mSv. There is no guarantee that patients will personally benefit from inclusion in this study. Patients undergo a more thorough screening than non-study patients and may benefit from this increased surveillance. Information gathered in this study may benefit others undergoing THA with uncemented components.

1. INTRODUCTION AND RATIONALE

Aseptic loosening of the acetabular component of hip implants in total hip arthroplasty (THA) remains one of the main causes of long-term implant failure and revision (LROI, 2023; NJR, 2023; NJRR, 2023). Aseptic loosening is often induced by wear of polyethylene liners, causing osteolysis around the implant. Highly cross-linked polyethylene liners have been developed to reduce the risk of wear. Ceramic has a higher stiffness and ceramic-on-ceramic (CoC) shows even lower wear rates compared to ceramic on polyethylene. However, the inelasticity of a CoC bearing might hamper a natural load transfer to the bone, potentially causing increased micromotion and thereby affect implant stability in press-fit THA (Small et al., 2013; van Loon et al., 2023).

The Delta-TT cup and H MAX S stem have been developed, aiming to optimize initial stability and osseointegration of the implant (LimaCorporate, Villanova San Daniele del Friuli, Italy). Radiostereometric Analysis (RSA) is a very accurate measurement technique to determine micromotion of the implant relative to inserted tantalum markers in the surrounding bone and has been the recommended means in evidence-based phased introduction of new implants (Swierstra et al., 2011). It is believed that early RSA migration patterns at 2 years postoperatively can predict implants at risk for long-term aseptic loosening (Nieuwenhuijse, Valstar, Kaptein, & Nelissen, 2012; Pijls et al., 2012; Streit et al., 2016)

In our initial Delta-TT study, we used RSA imaging to compare early migration patterns of the Delta-TT cup and H MAX S stem between polyethylene and ceramic liners. A trend towards increased migration was observed in Delta TT cups combined with ceramic liners, however between-group effects were small and not statistically significant. The 2-year results showed stabilization of Delta-TT cups within 6 months, regardless of liner type (Klaassen et al., 2022). Similarly, the 5-year results showed comparable migration patterns of the Delta TT cup and H MAX S stem between ceramic and polyethylene liners. These results indicate that after initial migration, implants in both groups showed secondary stabilization, which is promising for long-term survival of the implant.

In this study, we will investigate the long-term migration patterns of the Delta-TT cup and compare these outcomes between polyethylene and ceramic liners. Similar to the 2- and 5-years results, good stability is hypothesized at 10-years postoperatively, regardless of liner type. The secondary objectives are to determine migration of the H MAX S stem at 10-years postoperatively and to evaluate implant survival, signs of osteolysis, clinical outcomes and patient-reported outcome measures (PROMs) for the Delta-TT cup and H MAX S stem, comparing outcomes between the ceramic and polyethylene group.

Finally, we will compare the survival data at 10-years postoperatively with the predicted survival at 2-years postoperatively using the thresholds presented in the literature (Nieuwenhuijse et al., 2012; Pijls et al., 2012; Streit et al., 2016). The aim is to quantify how well RSA analysis at 2-years predicted survival for the uncemented press-fit components used in this study.

This will be the first study to evaluate long-term migration patterns of uncemented components, compared between ceramic and polyethylene liners. Besides, this study will investigate long-term stability and survival of the Delta-TT cup and H MAX S stem. The results will contribute to the understanding of long-term survival of uncemented components.

2. OBJECTIVES

Primary Objective:

- To compare long-term stability of the Delta TT cup between ceramic and polyethylene liners, by means of RSA at 10-years postoperatively.

Secondary Objectives:

- To compare long-term stability of the H MAX S stem between ceramic and polyethylene liners, by means of RSA at 10-year postoperatively.
- To measure implant survival rates, reasons for revision and radiographic signs of osteolysis and compare these outcomes between ceramic and polyethylene liners.
- To compare clinical outcomes and patient-reported outcome measures (PROMs) for the Delta TT cup with H MAX S stem, between the ceramic and polyethylene group.
- To compare the survival data at 10-years postoperatively with the predicted survival at 2-years postoperatively using the thresholds presented in the literature. The aim is to measure the predictive value and quantify how well RSA analysis at 2-years predicted survival for the uncemented press-fit components used in this study.

3. STUDY DESIGN

This study is a long-term follow-up of the Delta-TT trial, in which 52 patients who underwent unilateral primary hip arthroplasty were randomized between a polyethylene liner (n = 25) and a ceramic liner (n = 27). The initial study included RSA imaging at baseline (within 3 days postoperative before weight bearing) and at 6 weeks, 3 months, 6 months, 1 year, 2 years and 5 years postoperatively. At these same timepoints PROMs were documented, including EuroQol 5D-3L (EQ5D-3L), Hip disability and Osteoarthritis Outcome Score-Physical function Short form (HOOS-PS), Numeric (Pain) Rating Scale (NRS) and Oxford Hip Score. At 5-years follow-up, 1 patient was withdrawn from the study, the remaining 51 patients will be invited to participate in the RSA-10 follow-up study.

In this 10-year follow-up, 3D translations and rotations by means of RSA X-rays are used to determine the long-term stability of the Delta-TT cup and the H MAX S stem for the polyethylene and ceramic liner group. Implant survival is determined through revision rates. Furthermore radiographic signs of aseptic loosening will be investigated for both the cup and stem, by evaluating radiolucency on anteroposterior (AP) and lateral (LAT) X-rays. The acetabular zones will be evaluated as described by DeLee and Charnley and the zones around the stem will be evaluated using the Gruen zones (DeLee & Charnley, 1976; Gruen, McNeice, & Amstutz, 1979; Zicat, Engh, & Gokcen, 1995). PROMs will be collected to determine long-term functional outcome of the implants. Instead of EQ5D-3 the more recent EQ5D-5L will be used, because it shows a reduced ceiling effect compared to the EQ5D-3L version (Feng, Devlin, & Herdman, 2015; Herdman et al., 2011). To compare these EQ5D-5L scores to the values of the initial study they will be translated to the EQ5D-3L scores (van Hout et al., 2012). In addition, clinical outcomes such as squeaking of the hip will be collected. An overview of the 10-year follow-up measurement methods is provided in table 1.

Table 1: timeline of measurements.

Outcome measurements 10-year postoperatively
RSA röntgenanalysis
Survival
AP and LAT X-rays
Numeric (Pain) Rating Scale (NRS)
EQ-5D-5L
HOOS-PS
Oxford Hip Score
Other clinical outcomes

All patients were included in the initial study, between October 2014 and February 2016 and will therefore reach the 10-year mark between October 2024 and February 2026. An overview of the study timeline is provided in table 2.

Table 2: study timeline.

Study phase	2024				2025				2026			
	Q1	Q2	Q3	Q4	Q1	Q2	Q3	Q4	Q1	Q2	Q3	Q4
Preparation												
Patient inclusion and data collection												
Data analysis and reporting												

4. STUDY POPULATION

4.1 Population (base)

All participants in this study were already enrolled in the initial Delta-TT trial, between October 2014 and February 2016. All patients were included in the OLVG hospital (Amsterdam, the Netherlands) and will be contacted to participate in the follow-up trial. Patients will be informed about the results of the 2- and 5-year follow-up and the study specifics for the 10-year follow-up. They will also be given the opportunity to ask questions and to take time to think about their decision. If patients do not wish to participate and are willing to share their reason why, this will be recorded in the screening log.

4.2 Inclusion criteria

The inclusion criteria for the initial Delta-TT study were:

- A. Patients scheduled to undergo primary total hip replacement.
- B. Patient is able to understand the meaning of the study and is willing to sign the ethical committee (EC) approved, study-specific Informed Patient Consent Form (ICF).
- C. Ability and willingness to follow instructions and to return for follow-up evaluations.
- D. The subject is a male or non-pregnant female between 18 and 75 years of age.

We anticipate that some of the patients from the initial study, whether in the ceramic insert group or the polyethylene group, may have subsequently undergone a THA revision. The frequency of THA revisions holds significant importance as an outcome measure for this study. These patients will therefore also be requested to provide written informed consent. If consent is given, these patients will be included in the study but will not be eligible for RSA imaging and X-rays. All other data will be collected.

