4.4 Sample size calculation

RSA studies have a high degree of sensitivity and accuracy of measurements (Valstar et al., 2005). Therefore, relatively small patient groups are sufficient to detect between group differences. Sample size calculations in the initial study are based on a standard deviation of 0.3mm translation and 0.8° rotation for the uncemented cup (Baad-Hansen et al., 2011). At 10 years, we aim to include all 51 patients that were still included in the previous study at 5-years follow-up. Using Cohen's d, a difference of 1SD can be detected with 80% power and alfa 0.05, based on 16 patients in each group (<https://www.sealedenvelope.com/power/continuous-superiority/>).

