10. STATISTICAL ANALYSIS

In general, data will be summarized by treatment group. For parameters represented by continuous variables, the summaries will consist of the mean and 95% confidence intervals. Continuous outcome variables will be analysed with parametrical statistical techniques, unless the normality assumption does not seem reasonable for the data, in which case non-parametric techniques will be considered.

For categorical variables, the number and percent in each category will be presented and will be analysed. Descriptive statistics for demographic, efficacy, and safety variables will be provided in tables. A two-sided 0.05 alpha level will be used.

Descriptive statistics and statistical comparisons for important demographic, efficacy, and safety variables will be provided in tables. A two-sided 0.05 alpha level will be used.

To assess cup and stem migration a mixed model analysis will be performed, with bearing (PE vs. CE) as the primary independent value of interest. Primary outcome will be the effect of bearing over the 10-year follow-up period on implant migration. Group differences will be separately analysed at each time point including time as a categorical factor variable and a time-by-group interaction term. Differences are considered significant for p-values below 0.05.

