10.1 Primary study parameter(s)

The main study parameter is migration of the Delta TT cup compared between a polyethylene and ceramic insert by means of RSA imaging at 10 years postoperative. RSA data will be analyzed using mixed model analysis with bearing (CE vs PE) as a primary independent value of interest.

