10.3 Other study parameters

- 10-year implant survival rates will be investigated for both the Delta TT cup and H MAX stem. We hypothesize that survival for both components is >95% at 10 years

postoperatively. Since this study is not powered for survival analysis, the differences between the groups will be reported, but not statistically tested.

- For determining radiological signs of aseptic loosening, radiolucent lines (RLs) are examined on lateral and anteroposterior X-rays. Around the cup, RLs are assessed in the three zones defined by DeLee and Charnley (DeLee & Charnley, 1976). Around the stem, RLs are examined in the seven zones defined by Gruen (Gruen et al., 1979). An RL is defined as such if the maximum width is equal to or greater than 1 mm, similar to previous studies (Carli, Warth, de Mesy Bentley, & Nestor, 2017; Hasler et al., 2021; Oishi et al., 2021). A Chi-square test is used to compare the number of cases with one or more RLs between the polyethylene liner group and the ceramic liner group, for both the acetabular cup and the femoral stem. If there are fewer than 10 observed cases with one or more RLs in one of the two groups, the Fisher's exact test is used, which is valid for all sample sizes (Kim, 2017).
- Patient reported outcomes up until 10 years postoperatively will be presented with means and 95% confidence intervals and visually presented in graphs.
- Survival data at 10-years postoperatively will be compared with the predicted survival at 2-years postoperatively using the thresholds presented in the literature. The aim is to measure the predictive value and quantify how well RSA analysis at 2-years predicted survival for the uncemented press-fit components used in this study.

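### Section 4.2 bars every revised patient from 10-year imaging although endpoints are per component: retained cups and stems are lost, and the 10-year contrasts are conditional on no revision

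*Protocol*

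**What the plan says.** Section 4.2 expects that some patients in either liner group "may have subsequently undergone a THA revision". They are asked for consent, and then "these patients will be included in the study but will not be eligible for RSA imaging and X-rays"; for the rest, "All other data will be collected". The rule does not ask which component was revised, or why.

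The endpoints are set per component. Cup migration is primary (8.1.1, 10.1) and stem migration secondary (8.1.2, 10.2). For the cup, "RSA data will be analyzed using mixed model analysis with bearing (CE vs PE) as a primary independent value of interest". Section 10 makes the primary outcome the bearing effect over the whole 10-year follow-up, with time as a categorical factor and a time-by-group interaction. RSA was taken from baseline to 5 years in the initial trial (section 3).

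Radiolucency is compared for cup and stem separately (10.3): "A Chi-square test is used to compare the number of cases with one or more RLs between the polyethylene liner group" and the ceramic group, with Fisher's exact test when cases are few. How a revised hip counts in that table is not stated.

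Revision, its reason and survival time come from the national register (8.1.3). Group differences in survival are reported but not tested (10.3), with this expectation: "We hypothesize that survival for both components is >95% at 10 years". There is one visit and no follow-up after it (9.2).

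**The concern.** Two separate things follow from the rule.

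First, measurable data are given up. RSA locates an implant against bone markers and its own postoperative baseline (8.3). After a stem-only revision the original cup can still be measured in that way, and after a cup-only revision so can the original stem, provided their markers remain stable. Section 4.2 bars both. No analysis plan can restore an image that was not made at the only visit.

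Second, the hips that did worst may be absent from both 10-year comparisons. A component revised for loosening has no 10-year migration value and no radiolucency reading. If such revisions were more common with one liner, the contrast among unrevised hips would understate the difference. The protocol's rationale makes this relevant: it suggests that a stiff ceramic bearing may increase micromotion, and it reports a non-significant trend to more migration with ceramic liners (section 1).

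**Working it through.** **Inputs from the protocol.** 25 polyethylene and 27 ceramic randomized, 1 withdrawn by 5 years, 51 invited (section 3; the arm of the withdrawal is not stated, so 25 v 26 is assumed). SD 0.3 mm for cup translation (4.4). Alpha: "A two-sided 0.05 alpha level will be used" (section 10). Survival above 95% per component (10.3).

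**1. The plan's own figure.** Section 4.4 states that "a difference of 1SD can be detected with 80% power and alfa 0.05, based on 16 patients in each group". The normal approximation gives n = 2 × (1.960 + 0.842)² / 1² = 15.7, so 16 per group, with power 0.807. It reproduces. (By t-test, n is 17 and power at 16 is 0.781.)

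**2. How many revisions.** 5% of 51 is 2.55. Survival above 95% therefore allows at most 2 of 51 per component (2/51 = 3.9%; 3/51 = 5.9%), or at most 4 patients if cup and stem revisions never coincide. If the true risk were exactly 5%, the chance of at least one revision of a given component would be 0.93, and of at least three 0.47.

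**3. Power is not the issue.** For a 1 SD difference (t-test): 93.8% with 25 v 26, 92.3% with 23 v 25, 88.5% with 20 v 22.

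**4. Shift in the observed 10-year mean (assumed scenarios).** If k of 26 ceramic cups are revised and each would have had m mm more migration than the rest, leaving them out lowers that arm's mean by k × m / 26.

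| k | m = 1 mm | m = 2 mm | m = 3 mm |
|---|---|---|---|
| 1 | 0.04 mm (0.13 SD) | 0.08 mm (0.26 SD) | 0.12 mm (0.38 SD) |
| 2 | 0.08 mm (0.26 SD) | 0.15 mm (0.51 SD) | 0.23 mm (0.77 SD) |
| 3 | 0.12 mm (0.38 SD) | 0.23 mm (0.77 SD) | 0.35 mm (1.15 SD) |

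The row k = 3 already breaks the survival hypothesis. For scale, the 95% CI half-width for the group difference is 2.01 × 0.3 × √(1/25 + 1/26) = 0.17 mm.

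**5. What the mixed model recovers.** The table describes observed 10-year values, not the planned model. A simulation addressed the model (all assumed: visits at 2, 5 and 10 years, SD 0.3 mm, correlation 0.8, 25 v 26, no true difference among other hips, failing ceramic hips 2.0 mm worse at 10 years and unobserved then; 4,000 runs). Visible early means an excess of 0.6 mm at 2 years and 1.2 mm at 5 years.

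| k | Failure pattern | Full-data difference (mm) | Unrevised hips only (mm) | Likelihood model with earlier visits (mm) |
|---|---|---|---|---|
| 1 | visible early | 0.076 | −0.001 | 0.030 |
| 1 | after 5 years only | 0.076 | 0.000 | −0.001 |
| 2 | visible early | 0.154 | 0.001 | 0.062 |
| 2 | after 5 years only | 0.156 | 0.003 | 0.003 |

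With two early-visible failures the model recovers 0.062/0.154 = 40% of the difference. With failure after the 5-year image it recovers practically none.

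**6. Radiolucency.** This is one comparison at 10 years. If 2 of 26 ceramic cups were revised for loosening and no other ceramic cup had a line (assumed), the table would show 0/24 = 0%. Counting the failures gives 2/26 = 7.7%.

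**The case against.** A reader might infer that stability is judged on survivors only. The protocol does not support that. Section 4.2 stops new imaging only; no section removes RSA taken before revision, and the model in section 10 spans the whole follow-up. The statement holds for the 10-year RSA readings and the radiolucency table, not for the migration analysis as a whole.

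Failures are not hidden either. Revision rates and reasons are a stated objective (section 2), are reported by group (10.3), and are related to 2-year migration (8.1.3). An excess with one liner would appear beside the migration result. A removed component cannot be measured under any rule, so part of the loss is unavoidable.

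A reader might also infer that the liner with more revisions must look falsely stable. That requires revision for loosening; revision for another reason need not favour either liner. Nor is a retained cup after liner exchange straightforward primary data, because the patient may no longer carry the randomized bearing. Recasting the radiolucency outcome as a composite with revision would change a defined endpoint, which is a matter of preference.

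Handling of missing 10-year values may stand in an analysis plan that is not shown. That weakens the call for sensitivity analyses. It does not touch the imaging rule, which only the protocol governs.

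**Conclusion.** The point holds in two parts. The per-patient bar does not fit per-component endpoints and needlessly loses original cups or stems that could still be measured; this follows from the text alone. The 10-year migration contrast and the radiolucency test are also conditional on no revision, with partial protection from earlier RSA for migration and none for radiolucency.

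The size is unknown. Within the survival hypothesis the numbers are small: at most 2 of 51 per component. If both fell in the ceramic arm with 1 to 3 mm excess migration, the shift in that arm's observed mean would be 0.08 to 0.23 mm (0.26 to 0.77 SD), less whatever the mixed model recovers. If revisions were none, balanced, or not for loosening, it could be negligible. The revision counts by arm, the excess migration and the correlation are assumptions, not protocol figures. Loss of power is minor.

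**What to change.** **Section 4.2.** Replace the per-patient bar with a component rule: only a component that has been removed is excluded from RSA and radiolucency assessment, and an original component still in situ is imaged as planned. Flag patients whose liner was exchanged, keep them in their randomized group, and leave them out in a sensitivity analysis.

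**Sections 10.1 and 10.2.** Add a sensitivity analysis of 10-year cup and stem migration in which components revised for aseptic loosening take the worst rank. State for each axis which direction counts as worst; 8.1.3 already names proximal translation for the cup and subsidence for the stem.

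**Section 10.3.** Add a sensitivity version of the radiolucency comparison that counts components revised for aseptic loosening as cases. The primary definitions stay unchanged.

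**Cost.** A protocol amendment, images for a few more patients at the dose the study already accepts, and a little more analysis. The imaging change helps only patients not yet seen at 10 years; the analysis changes can be made at any time before the data are analysed.
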